
 
For the secondary analysis of Hgb change from baseline to Week 52, a mixed model repeated measures (MMRM) approach will be used with an unstructured covariance matrix to compare the difference in means between arms. The model will be fitted to Hgb data collected after baseline up to Week 52, excluding values collected during the stabilization period (Day 1 to Week 28). The model will include factors for treatment, time, prognostic randomization stratification factor (region, see Section 5.3), baseline Hgb and the baseline Hgb by time and treatment by time interaction terms. Analyses will be done with the MIXED procedure in SAS, using the Kenward-Roger option to estimate denominator degrees of freedom and standard errors. This analysis will be performed using all available Hgb values (on and off-treatment) and separately using evaluable Hgb values only (see Section 14.6.3). In the analysis using all available Hgb values, subjects who withdraw from the study before Week 52 are considered to be missing at random and in the analysis using evaluable Hgb values, subjects who permanently discontinue study treatment before Week 52 are assumed to be missing at random.
 
For the analysis of % time in range, the method by Rosendaal [Rosendaal, 1993] will be used to calculate the percentage of time (days) a subject's Hgb is below, within and above the Hgb analysis range of 10 to 11.5 g/dL during the EP (Weeks 28-52). A van Elteren test (stratified Wilcoxon rank sum test) will be used to compare the percentage of time in range between treatment arms, adjusting for treatment and the prognostic randomization stratification factor (see Section 5.3). This analysis will be performed using evaluable Hgb
 

values only. Hodges-Lehmann estimate of the treatment difference will be used to assess non-inferiority in % time in range.
 
 
For the Hgb responder analysis, mean Hgb during the EP will be defined as in the while on-treatment evaluable Hgb supportive analysis (Section 14.6.3). Responders will be subjects with a mean Hgb during the EP that falls within the Hgb analysis range of 10-11.5 g/dL. A Cochran-Mantel-Haenszel (CMH) chi-squared test, adjusting for treatment and the prognostic randomization stratification factor (region as randomized, see Section 5.3), will be used to compare the number and % of responders between the treatment groups.
 

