
 
• The difference in change from baseline in BP (SBP, DBP, and MAP) at Week 52 will be analyzed with a mixed model repeated measures (MMRM) approach with an unstructured covariance matrix to compare the difference in means between arms. The models will be fitted to scheduled BP data collected after baseline up to Week 52 (including Week 52 visit). Models will be run four times: 
 
○ On-treatment BP values only, excluding values collected during the stabilization period (post-baseline up to but excluding Week 28 visit).
 
○ On-treatment BP values only, including values collected during the stabilization period.
 
○ On- and off-treatment BP values, excluding values collected during the stabilization period.
 
○ On- and off-treatment BP values, including values collected during the stabilization period.
 
 
 
• The models will include factors for treatment, time, prognostic randomization stratification factor (Region, see Section 5.3), baseline BP parameter and the baseline BP parameter by time and treatment by time interaction terms. Analyses will be done with the MIXED procedure in SAS, using the Kenward-Roger option to estimate denominator degrees of freedom and standard errors. For analyses using on- and off-treatment values, subjects who withdraw from the study before Week 52 are considered to be missing at random and in the analysis using on-treatment values only, subjects who permanently discontinue study treatment before Week 52 are assumed to be missing at random.
 
• The difference in change from baseline in BP (SBP, DBP, and MAP) at the derived end of treatment (see Section 14.6.4) will be analyzed with an ANCOVA model including terms for treatment, prognostic randomization stratification factor (Region, see Section 5.3) and the corresponding baseline BP parameter. This analysis will be performed using on-treatment BP values only.
 
• The number of on-treatment BP exacerbation events per 100 patient years will be calculated (see Section 14.6.4). Confidence intervals for the rate per 100 patient years will also be reported. For within group rates and the ratio of model estimated exacerbation rates, the point estimates, two-sided 95% confidence intervals, and one-sided p-value for the treatment group
 

CONFIDENTIAL

204837

Secondary Safety Statistical Analyses: Blood Pressure

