
End of Treatment Value
 
 
• Only defined for subjects with a non-missing treatment start date
 
• Hgb, iron, transfusion and PRO parameter: the latest value on or before the treatment stop date + 1 day.
 
• Blood pressure, central laboratory, and vital signs parameters: the latest value on or before the last non-zero dose date + 1 day.
 

CONFIDENTIAL

204837

Study Completion/Withdrawal Date

 
Date of withdrawal for subjects withdrawing (i.e., subjects who actively withdraw or are deemed lost to follow-up) from study or date of completion of study for subjects who complete the study. 
 
Note: Subjects who die while on study are considered as having completed the study
 
 
 

Planned/Actual Visit Dates

 
Planned/actual visit dates will be defined as follows: 
 
Week 28 date: Non-missing Week 28 visit start date (from SV domain), otherwise randomization date + 28*7
 
Week 36 date: Non-missing Week 36 visit end date (from SV domain), otherwise randomization date + 36*7
 
Week 52 date: Non-missing Week 52 visit end date (from SV domain), otherwise randomization date + 52*7
 
 
 

Stabilization Period
Defined as the period between and including the randomization date + 1 day - <Week 28 visit, using planned/actual dates.
Alternative Evaluation Period (Alt. EP)
Defined as the period between and including Week 28 visit – Week 36 visit, using planned/actual dates.
Evaluation Period (EP)
Defined as the period between and including Week 28 visit – Week 52 visit, using planned/actual dates.
Study Day

 
Calculated as the number of days from randomization date: 
 
Ref Date = Missing → Study Day = Missing
 
Ref Date < Randomization Date → Study Day = Ref Date – Randomization Date
 
Ref Date ≥ Randomization Date → Study Day = Ref Date – (Randomization Date) + 1
 
 
 

Treatment Day

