### 14.6.3. Efficacy

#### 14.6.3.1. Hemoglobin Endpoints

Hemoglobin Values
Central Laboratory and HemoCue Hgb Values

 
When source of Hgb measurement is not specified: 
 
For reporting purposes, central laboratory Hgb values will be used, unless otherwise specified. However, if a central laboratory Hgb value is missing, a corresponding non-missing HemoCue Hgb value will be used. This approach will be used for the primary Hgb analysis.
 
 
 
Some displays may be created for either central laboratory Hgb values only or HemoCue Hgb values only. The central laboratory summary will be considered the primary summary in this case.
 

Evaluable Hemoglobin Values

 
Evaluable Hgb values are on-treatment Hgb values (see Section 14.4.1) that are not taken within the 8 weeks following a red blood cell transfusion, a whole blood transfusion, or a non-randomized ESA treatment which occurs on or after the randomization date.
 
Red blood cell transfusions, whole blood transfusions and non-randomized ESA treatments occurring on or after the randomization date are identified by comparing the start and stop date of the respective transfusion or ESA concomitant medication record to the randomization date.
 

Imputed Hemoglobin Values

 
For each missing value between baseline to Week 52 (inclusive), 200 imputed values will be generated using the multiple imputation method (see Section 7.1.5). The average of these 200 imputed values will be used as the value for this missing value in the summary tables and figures.
 

CONFIDENTIAL

204837

Hemoglobin Values					

 
For primary efficacy Hgb analysis and the corresponding subgroup analyses using all available observed and imputed Hgb values (on and off-treatment), Rubin's rules [Rubin, 1987] will be used to combine results of the imputed datasets using SAS PROC MIANALYZE procedure.
 
					
EP Hemoglobin Value for Primary Hgb Analysis					

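### The Week 52 Hgb non-inferiority MMRM uses only Week 28 to 52 values, so for participants lost to it before Week 28 the missing-at-random assumption ignores their on-study Hgb

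*SAP*

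**What the plan says.** SAP 7.3.1 (Hgb Variability, Model Specification) compares the arms on Hgb change at Week 52 with an unstructured-covariance MMRM "fitted to Hgb data collected after baseline up to Week 52, excluding values collected during the stabilization period". SAP 14.6.1 defines that period: "Defined as the period between and including the randomization date + 1 day - <Week 28 visit, using planned/actual dates". Day 1 falls outside it, and the model keeps "baseline Hgb and the baseline Hgb by time and treatment by time interaction terms", together with treatment, time and region.

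Two runs are planned: "This analysis will be performed using all available Hgb values (on and off-treatment) and separately using evaluable Hgb values only". Each has its own missing-data statement. In the all-available run, "subjects who withdraw from the study before Week 52 are considered to be missing at random". In the evaluable run, "subjects who permanently discontinue study treatment before Week 52 are assumed to be missing at random". SAP 14.6.3.1 settles who can appear in the second run: "Evaluable Hgb values are on-treatment Hgb values", with further exclusions after transfusion or non-randomized ESA.

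The lower confidence limit is compared with -0.75 g/dL. SAP 5.5 gives the additional secondary endpoints no multiplicity adjustment.

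**The concern.** An MMRM deals with dropout by conditioning on the outcomes that are in the model. A participant with no Week 28 to 52 value supplies none, so the model treats that person as exchangeable with others of the same arm, region and baseline Hgb.

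The protocol links stopping to later Hgb. Under 7.9 (Table 8) and 8.1, rescue evaluation begins at Week 4, and Hgb still below 9 g/dL after the initial intervention leads to permanent discontinuation. In the evaluable run, a participant rescued before Week 28 drops out of the model together with the low values that preceded the stop. If one arm has more such losses, its remaining participants look better at Week 52.

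The SAP uses the earlier data elsewhere. The primary imputation (7.1.5.1) conditions on prior scheduled Hgb from before Week 28. The PGI-S MMRM (Section 9) uses all post-baseline data. The blood pressure MMRM (8.1) is run both ways, including "On-treatment BP values only, including values collected during the stabilization period". Only the Hgb MMRM lacks an inclusive version, and no reason is given. The planned tipping-point analyses concern the evaluation-period mean, so this Week 52 model has no missing-data sensitivity analysis.

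**Working it through.** **1. Visits used.** From the Schedule of Activities:
- Excluded: Weeks 2, 4, 6, 8, 12, 16, 20, 24 = 8 visits.
- Kept: Weeks 28, 32, 36, 40, 44, 48, 52 = 7 visits. So 8 of 15 scheduled post-baseline visits are dropped.
- Unstructured covariance parameters: 7×8/2 = 28 as planned; 15×16/2 = 120 with all visits.

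**2. Who has no outcome in the model.**

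| Event before Week 28 | All-available run | Evaluable run |
|---|---|---|
| Withdraws from the study | none | none |
| Stops treatment, stays in follow-up | contributes (Weeks 28, 40, 52) | none |

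The follow-up visits are in Protocol 8.1.1. SAP 14.5.2 analyses them with the corresponding scheduled weeks.

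**3. The plan's own figures.** Protocol 10.1.1 gives N = 402 (268:134), SD 1.5, difference 0, margin -0.75 and up to about 10% without evaluation-period (EP) Hgb.
- Evaluable: 402×0.9 = 361.8, about 241 + 121.
- Half-width: 1.96×1.5×√(1/241 + 1/121) = 0.328 (stated 0.33).
- Largest passing deficit: -0.75 + 0.328 = -0.422 (stated -0.42).
- Power: 99.4% (stated above 90%).
- Without EP Hgb: 0.10×402 ≈ 40 participants.

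These reproduce, but they refer to the primary endpoint. No figure is stated for the Week 52 MMRM.

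**4. Size of the bias.** The documents give no visit correlation and no dropout rates by arm or by Hgb, so everything here is assumed. Settings: 268:134; visit SD 1.2; correlation 0.35 + 0.65×0.97^t for visits t weeks apart; treatment difference reached by Week 24; 400 trials per scenario. Dropout is monotone. Where it is low-Hgb driven, the hazard rises by a factor e per 1 g/dL lower Hgb at the last observed visit. The fit is maximum likelihood with treatment by time, baseline by time and unstructured covariance; region is omitted. A lost participant supplies nothing later, which mimics study withdrawal, or a treatment stop in the evaluable run.

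Bias is the mean estimate minus the true difference. Error is the proportion of trials passing non-inferiority when the truth is -0.75 (nominal 0.025, empirical SE used). Monte Carlo SE is about 0.12/√400 = 0.006 for bias and √(0.025×0.975/400) = 0.008 for error near nominal.

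| Loss before Week 28 | Lost, dapro / epoetin | Bias, Wk 28-52 | Bias, Wk 2-52 | Error, Wk 28-52 | Error, Wk 2-52 |
|---|---|---|---|---|---|
| Random, both arms | 9.5% / 9.6% | -0.001 | -0.001 | 0.020 | 0.020 |
| Low-Hgb, same rule in both | 12.4% / 9.0% | +0.017 | +0.006 | 0.035 | 0.033 |
| Low-Hgb dapro, random epoetin | 12.5% / 9.4% | +0.025 | -0.007 | 0.043 | 0.022 |
| Same, less epoetin loss | 12.2% / 4.9% | +0.030 | -0.001 | 0.050 | 0.015 |
| Same, heavier loss | 21.7% / 18.1% | +0.050 | -0.007 | 0.060 | 0.022 |
| Heavier, slower correlation decay (0.99) | 20.9% / 18.5% | +0.042 | +0.006 | 0.065 | 0.035 |
| Heavier, SD 1.5 | 19.3% / 18.3% | +0.068 | -0.005 | 0.052 | 0.022 |
| Heavier, less epoetin loss | 21.6% / 9.6% | +0.061 | +0.006 | 0.085 | 0.037 |
| Low-Hgb dapro, high-Hgb epoetin | 21.5% / 15.7% | +0.107 | +0.011 | 0.135 | 0.035 |

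With a true difference of 0 and heavier low-Hgb loss on daprodustat (15.8% / 18.3% lost), bias was +0.035 for Weeks 28-52 and -0.001 for Weeks 2-52. Both fits passed in all 400 trials. Standard errors were practically the same for the two fits in every scenario.

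A separate simulation had 30,000 participants per arm, no true difference, and the participants with the lowest Week 12 to 24 Hgb stopping before Week 28. With 10% vs 5%, 15% vs 5% and 20% vs 10% stopping on daprodustat vs epoetin, the EP-only estimates were +0.023, +0.047 and +0.050. Using all visits gave -0.008, -0.009 and -0.004.

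**The case against.** **Reach.** A reader might infer that everyone who leaves or stops before Week 28 disappears and that all earlier Hgb is thrown away. The documents do not support this. A rescued participant stays in the study and can supply up to three scheduled EP values to the all-available run, and baseline Hgb remains as a covariate, alone and by time. The rescue rule also continues beyond Week 28, and for rescues in the EP the preceding EP values are in the model.

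**Repair.** A reader might also infer that restoring Weeks 2 to 24 makes MAR true. It makes MAR more plausible and no more. Rescue is triggered by HemoCue readings, while the analysis prefers central laboratory values. Deaths, transplants, modality changes and consent withdrawals need not follow Hgb. The inclusive fit is unbiased in the simulations partly because dropout was generated from the Hgb values it uses.

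**Consequence.** The endpoint is nominal, and SAP 7.3.1 uses the margin for reference. The primary analysis imputes from all prior scheduled Hgb and has a tipping-point analysis. Time to stopping for rescue is a separate secondary endpoint. Missing EP data are already tabulated for the primary and evaluable analyses. All of this stands and limits the importance of the point.

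**Design.** Excluding titration data can be defended on the ground that Week 52 should reflect the stabilized dose. But with treatment by time, baseline by time and unstructured covariance, earlier visits impose no trajectory on Week 52; they inform it only through covariance. The larger matrix is a real cost.

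**Conclusion.** The point holds within limits. In both runs for study withdrawals before Week 28, and in the evaluable run for treatment stops before Week 28, the model has no outcome for the participant, and its MAR assumption is stronger than the SAP wording suggests.

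The bias runs in favour of the arm with more early low-Hgb loss. It was about 0.02 to 0.05 g/dL in most assumed scenarios, which is 3% to 7% of the margin (0.02/0.75 and 0.05/0.75). It reached 0.06 to 0.07 in two scenarios with about 20% lost on daprodustat, and 0.11 only when the two arms lost opposite kinds of participant. One-sided error at the margin rose to about 0.04 to 0.09 with low-Hgb loss on daprodustat only, and to 0.135 in the extreme case. Loss unrelated to Hgb gave no bias. All of this depends on dropout rates, mechanisms and correlations that the documents do not supply.

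A reader might infer that the trial's non-inferiority conclusion is in doubt. It is not: the primary analysis is unaffected, and with a true difference near zero even 0.11 is small beside the 0.42 g/dL deficit that the design tolerates. This is a minor to moderate point: a change worth making, not a condition for the plan's validity.

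**What to change.** Before unblinding, add to SAP 7.3.1 an MMRM fitted to all scheduled post-baseline visits from Week 2 to Week 52, with the same terms and unstructured covariance, for both the all-available and the evaluable run. Report its Week 52 contrast beside the EP-only fit, as is done for blood pressure. For each run, give the number of participants per arm with no EP record; most of this can come from the planned imputed-data and missing-data summaries.

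The convergence steps in SAP 5.4.2 are written for subgroup models and end with no model-adjusted result. Extend them to this model and say what stands if it still fails. One option is to analyse Week 52 in the multiply imputed data sets that the primary analysis already generates, which condition on all prior scheduled Hgb.

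The cost is a few sentences and two extra model fits, with no new data. The downside is a 15-visit covariance matrix (120 parameters against 28) and possible convergence work.

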### 5.4. Examination of Covariates, Other Strata and Subgroups

#### 5.4.1. Covariates and Other Strata

The list of covariates and other strata may be used in descriptive summaries and statistical analyses, some of which may also be used for subgroup analyses. Additional covariates and other strata of clinical interest may also be considered.

Category	Details
Strata	Regions listed in Section 5.3.
Covariates	Baseline Hgb (For the analysis of the primary endpoint and other analyses of Hgb-related endpoints)  For subgroup analyses, statistical models will be adjusted for the covariates used in the original analysis (randomization stratification factor and baseline hemoglobin), subgroup, treatment and treatment by subgroup interaction (see Section 5.4.2 for the subgroup variables.).

Randomization is stratified by the prognostic factor, region, which will be taken into account within the analysis models.

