
Model Results Presentation

 
For the MMRM analysis of change from baseline in Hgb, an LSMEANS statement will provide adjusted treatment group means and standard errors and a point estimate and two-sided 95% confidence interval for the adjusted mean treatment difference (daprodustat - rhEPO) at Week 52. The one-sided non-inferiority p-value for this test will be calculated.
 
For the responder analysis, the number and percentage of subjects with mean EP Hgb above, within and below the Hgb analysis range will be summarized by treatment group.
 
For the responder analysis, the number and % of responders by treatment group, difference in response rate (Dapro – rhEPO) and two-sided 95% CI will be provided along with the one-sided CMH p-value for the treatment group comparison.
 
The % time Hgb is above, in and below the Hgb analysis range (10-11.5 g/dL) during the EP will be summarized using mean, standard deviation, minimum, P25, median, P75, and maximum by treatment group.
 
For the percent time Hgb in analysis range for each treatment group, the stratified Mann-Whitey estimate of the treatment difference (daprodustat - rhEPO) and associated two-sided 95% CI [Kawaguchi, 2011] will be presented in addition to the one-sided superiority p-value from the van Elteren test. Hodges-Lehmann estimate of the treatment difference (daprodustat-rhEPO) and associated two-sided 95% CI will be presented.
 

Model Results Interpretation

 
For the MMRM analysis of change from baseline in Hgb, the NI margin used in the primary analysis of Hgb (-0.75 g/dL) will be used for reference in this comparison. Thus generating support for non-inferiority if the lower bound of the two-sided 95% CI is above -0.75 g/dL.
 
For the responder analysis, the one-sided CMH p-value will be compared to 0.025 to assess nominal significance.
 
For the percent time in range analysis, a NI margin of -15% will be used as a reference in this comparison, thus generating support for non-inferiority if the lower limit of the two-sided 95% CI of Hodges-Lehmann estimate is above -0.15. If non-inferiority is established, nominal superiority will be achieved if the one-sided p-value is < 0.025
 

Subgroup Analyses

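### The interval that decides non-inferiority for % time in range has no region stratification written, although the trial and the paired superiority test are stratified by region

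*SAP*

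**What the plan says.** SAP 7.3.1 (Hgb Variability) tests % time in range first for non-inferiority and then for superiority.

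- **Superiority.** "A van Elteren test (stratified Wilcoxon rank sum test) will be used to compare the percentage of time in range between treatment arms". Region, as the randomization stratum, is the stratifying factor in this test. Under Model Results Presentation, the accompanying Mann-Whitney estimate and its CI are also described as stratified.
- **Non-inferiority.** The Model Specification says that the "Hodges-Lehmann estimate of the treatment difference will be used to assess non-inferiority in % time in range". Model Results Presentation adds that the "Hodges-Lehmann estimate of the treatment difference (daprodustat-rhEPO) and associated two-sided 95% CI will be presented". Under Model Results Interpretation, "a NI margin of -15% will be used as a reference in this comparison", with support claimed if the "lower limit of the two-sided 95% CI of Hodges-Lehmann estimate is above -0.15".
- **Region.** SAP 5.4.1 says: "Randomization is stratified by the prognostic factor, region, which will be taken into account within the analysis models". SAP 5.3 lists five regions.

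None of the Hodges-Lehmann sentences names a stratum, a weighting or a method for the interval.

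**The concern.** A two-sample Hodges-Lehmann estimate named without qualification is the median of all pairwise differences between the arms, pooled over strata. A programmer following the text would produce that. The neighbouring Mann-Whitney estimate is called stratified and this one is not, which makes the pooled reading the natural one.

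The pooled interval carries between-region variation that stratified randomization has already removed from the treatment comparison. If regions differ in time in range, precision is lost at the step that must succeed before superiority is considered. The two steps for one endpoint would also treat region differently. The SAP's other two endpoint-level non-inferiority assessments, the primary ANCOVA and the Week 52 repeated-measures model, both include region.

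**Working it through.** **1. The plan's own figures.** Neither document gives a power, SD or precision for % time in range, so there is nothing to reproduce for this endpoint. The sizing for the primary endpoint in protocol 10.1.1 does reproduce. With 240 vs 120 evaluable, the half-width is 1.96 × 1.5 × √(1/240 + 1/120) = 0.329 g/dL (stated 0.33). The limiting difference is -0.75 + 0.329 = -0.421 (stated -0.42).

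**2. Inputs for this endpoint.**
- From the documents: 2:1 allocation, about 360 evaluable (protocol 5.2), five regions, margin -15 points, two-sided 95% CI.
- Assumed: 216 vs 108 analysed, which is 90% of 240 vs 120. SAP 14.6.3.1 defines percent time in range only for participants still on treatment after Week 28 with at least two evaluable values.
- Assumed: SD of about 32 points (taken as the within-region SD in the formulas below), allocation balanced within region, and a between-region SD b of 0 to 12 points.

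**3. Width.** The pooled variance is 32² + b² and the within-region variance is 32², so the approximate ratio of widths is √(1 + b²/32²). The simulated ratios come from inverting the Wilcoxon statistic (pooled) or the van Elteren statistic (stratified), with 500 to 800 trials per setting.

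| Region SD b (points) | Formula | Simulated, pooled / stratified |
|---|---|---|
| 0 | 1.000 | 0.99 to 1.00 |
| 5 | 1.012 | 1.01 |
| 8 | 1.031 | 1.03 to 1.06 |
| 12 | 1.068 | 1.07 to 1.14 |

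A separate simulation with 240 vs 120 and a within-region SD of 30 points gave 0.99 to 1.00 with no region effect, 1.02 when region explained 4% of the variance, and 1.11 at 14%.

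**4. Non-inferiority power at a true difference of -5, b = 8.** The distance to the margin is 10 points. With balanced allocation the difference has SE = 32 × √(1/216 + 1/108) = 3.77.
- Stratified: half-width 1.96 × 3.77 = 7.39; power Φ(10/3.77 - 1.96) = Φ(0.69) = 75.5%.
- Pooled: half-width 7.39 × 1.031 = 7.62; power Φ(10/3.77 - 1.96 × 1.031) = Φ(0.63) = 73.6%.
- Gain by normal approximation: 1.9 points.

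The simulations gave 71.0% to 72.6%, 78.5% to 81.2%, and 83.6% to 85.6%, depending on the assumed distribution. These are gains of 1.6, 2.7 and 2.0 points. With about 600 trials and 3.5% of them discordant, the Monte Carlo SE of a gain is about √(0.035/600) = 0.8 points, so the first decimal should not be relied on.

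**5. Type I error at -15, b = 8.** The pooled interval behaves as if its critical value were 1.96 × 1.031 = 2.02. The one-sided error is then about 1 - Φ(2.02) = 2.2%, against 2.5% nominal. The direction is conservative.

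**6. How often the conclusion changes.** At true differences of 0 or +6 points, the pooled and stratified intervals gave different non-inferiority conclusions in about 0 to 1% of trials. At -5 points they differed in 3 to 4% for b from 0 to 8, and in 4 to 9% at b = 12. About 3% differed even with no region effect, so leaving the method open leaves some borderline results open.

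**The case against.** **The SAP never says unstratified.** This stands. The Hodges-Lehmann sentence closes the same bullet that stratifies the van Elteren test, and SAP 5.4.1 could be read as covering it. A reader might infer that the sponsor chose to ignore region; the documents show only that region is not written for this estimate. If a stratified interval was intended, the text still needs to say so and name the method.

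**Other intervals are drafted the same way.** The responder difference CI sits beside a region-adjusted CMH test, and the Poisson and Wald rate intervals sit beside a region-adjusted Cox model. True, but none of those intervals decides a non-inferiority question.

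**A width gain is not assured.** This also stands. With no region effect the stratified interval is up to 1% wider. Both arms in every region are titrated by one algorithm to one target, which may keep regional differences small, and the documents give no estimate. The SAP does, however, call region prognostic.

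**The interval and the superiority test would not really conflict.** A reader might infer that they can contradict each other. Compared at zero, they disagreed in 2.5 to 19.5% of simulated trials at a true difference of +6 points, with the highest rates under strong assumed region effects. But the SAP judges the Hodges-Lehmann limit at -15% and van Elteren at zero. These are different null hypotheses, so the plan never makes that comparison.

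**A separate estimator is needed for non-inferiority.** Agreed. The margin is in points of time in range, a scale the Mann-Whitney estimate does not provide. The point concerns stratification of the Hodges-Lehmann estimate, not its use.

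**Conclusion.** The point holds as a modest matter of precision and consistency. As written, the non-inferiority interval for % time in range is the pooled Hodges-Lehmann interval, in a trial randomized and otherwise analysed by region. The cost is conditional: no loss with no region effect, about 1% extra width at a region SD of 5 points, and 3 to 6% at 8 points. That last case costs roughly 2 to 3 points of non-inferiority power at a true difference of -5. The SD, region effects, analysed numbers and true difference are all assumptions.

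It would be wrong to infer that a non-inferiority claim from this interval is invalid. The pooled interval tends to be conservative, so type I error is not inflated. Nor does anything confirmatory depend on it: SAP 5.5 leaves this endpoint outside the multiplicity hierarchy, and protocol 10.3.1 treats secondary analyses as exploratory. The primary and principal secondary tests are untouched. The change is a worthwhile near-free improvement, not the repair of an error.

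**What to change.** In SAP 7.3.1, state that non-inferiority for % time in range uses the Hodges-Lehmann estimate stratified by region as randomized (the weighted median of within-region pairwise differences). State that its two-sided 95% CI is obtained by inverting the van Elteren test, and that the -15% margin is applied to the lower limit of that interval. The interval, the superiority test and the randomization then use region in the same way, and no choice is left for after unblinding.

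The cost is one sentence of SAP text and a short custom program, with no new data. The downside is a negligible loss of precision, under 1% in width, if region turns out to have no effect.
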